**Protocol Amendment Summary of Changes Table**

DOCUMENT HISTORY	
Document	Date
ERX-963-001 Amendment 2	October 31, 2019
ERX-963-001 Amendment 1	March 7, 2019
ERX-963-001 Original (v1.1)	December 19, 2018
ERX-963-001 Original (v1)	November 15, 2018

**Amendment 2 (31-October-2019)****Summary of Amendment 2 Changes:**

This amendment modifies two exclusion criteria and one inclusion criterion. The endpoint of EEG is removed from the list of secondary endpoints. Additionally, the total number of completed participants is provided as an estimate rather than a maximum number, the interim analysis plan is clarified, the washouts between Periods 1-2 and Period 2-EOS visit are extended, and additional specifics around data collection for screen failures are provided.

Section # and Name	Description of Change	Brief Rationale
5.2 Exclusion Criteria #1	
Significant respiratory compromise as indicated by pulmonary function tests routinely conducted in the clinic including FVC <70% predicted.
 
Changed to
 
Significant respiratory compromise as indicated by clinical assessment (e.g. dyspnea) and by pulmonary function tests routinely conducted in the clinic.
	
Pulmonary function tests in the DM1 population may show a pseudo-restrictive pattern due to muscle weakness with parallel decrease in FEV-1 and FVC. The decline in respiratory function is typically gradual and patients may be able to compensate without significant respiratory distress. The change in the exclusion criteria removes the specific numerical FVC % predicted threshold and enables the investigator to make an overall assessment of respiratory function including both clinical and pulmonary function test assessments.

Section # and Name	Description of Change	Brief Rationale
5.2 Exclusion Criteria #3	
Diagnosis of symptomatic Restless Leg Syndrome or significant nocturnal hypoxias by nocturnal polysomnography performed within the last three years. Patients with obstructive or central sleep apnea who do not demonstrate compliance with non-invasive ventilation (NIV) strategy. Compliance will be determined by review of NIV device records from within the past 6 months and is defined as use of NIV for approximately 4 hours/night for 15 days out of a 1 month period. (Note: Patients with mild sleep apnea are eligible).
 
Changed to
 
3a. Diagnosis of symptomatic Restless Leg Syndrome OR
 
3b. Diagnosis of significant nocturnal hypoxias (moderate or severe obstructive or central sleep apnea) by nocturnal polysomnography performed within the last three years. Note: Patients with mild sleep apnea are eligible. Patients with a history of moderate to severe sleep apnea who are treated by and comply with non-invasive ventilation (NIV) are eligible to participate in the study and do not require repeat PSG prior to study entry. Patients with a history of moderate to severe sleep apnea who are not compliant with NIV treatment are not eligible. Compliance will be determined by review of NIV device records within the past 6 months and is defined as use of NIV for approximately <math>\geq</math> 4 hours/night for 15 days out of a 1 month period.
	
 
1. Clarify that Restless Leg Syndrome diagnosis does not require a polysomnography.
 
2. The intent of the exclusion criteria requiring a polysomnography within three years is to exclude patients who have sleep apnea treatable with non-invasive ventilation. This change clarifies that if a patient is compliant with non-invasive ventilation, then the patient is eligible to participate in the study without a prior polysomnography
 

3 Objectives and Endpoints	
Removed brain activity as a secondary objective and EEG as a secondary endpoint
 
Added text under Exploratory Objective To assess the effect of intravenously-administered ERX-963 vs. placebo on brain activity in patients with DM1
	The original intent was for EEG to be an exploratory objective; therefore the protocol has been corrected.

Section # and Name	Description of Change	Brief Rationale
5.1 Inclusion Criteria #1	
Participant must be at least 18 to 60 years of age, at the time of signing the informed consent.
 
Changed to
 
Participant must be at least 18 to 65 years of age, at the time of signing the informed consent.
	To allow inclusion of participants between age 60 and 65, as there is no rationale to support their exclusion.
9.5 Interim Analysis	
An interim analysis of efficacy parameters will be performed for administrative purposes after all patients from the first cohort have completed the study.
 
Changed to
 
A sponsor-unblinded interim analysis of efficacy parameters will be performed for administrative purposes after all patients from the first cohort have completed the study and may include participants from the second cohort who have completed the crossover portion of the study by the time of the interim analysis. An additional sponsor-unblinded analysis of selected parameters may be performed with additional participant data if necessary for administrative purposes. Details of the analyses will be provided in an interim analysis plan.
	
Clarify that the interim analysis of efficacy requires unblinding of the sponsor.
 
Clarify that the efficacy interim analysis may not be limited to results from the first cohort.
 
Added the option for an additional administrative analysis if necessary.

1.1 Synopsis	
A total of up to 14 participants completing
 
Changed to
 
An estimated total of 14 participants completing
	Removed the limit on the total number of completing participants, due to potential overlapping enrollment in a multi-center study
1.2 Schema	
Approximately 4 to 8 days washout
 
Changed to
 
Approximately 4 to 18 days washout
	Extension of the washout between periods 1-2 and the time between Period 2 and the End of Study visit will provide more flexibility for the participant. Extending by ten days should not impact the reliability of the study procedures.
4.1 Overall Design	
Approximately 4 to 8 days washout
 
Changed to
 
Approximately 4 to 18 days washout
	
8 Study Assessments	
Approximately 4 to 8 days after Period 1
 
Changed to
 
Approximately 4 to 18 days after Period 1
	

Section # and Name	Description of Change	Brief Rationale
8 Study Assessments	Approximately 4 to 8 days after Period 2 Changed to Approximately 4 to 18 days after Period 2	
5.4 Screen Failures	Added text If additional study procedures were performed during screening, information from these procedures should be recorded in the CRF.	To provide additional guidance for data entry expectations
1.2 Schema	Polysomnography within 3 years Added text If required  Washout 4-8 days Changed to Washout 4- 18 days	For alignment with revised Exclusion Criterion 5.3 and extended washout period
1.2 Schema	4-8 days after Period 2 Changed to 4- 18 days after Period 2	For alignment with extended time between Period 2 and End of Study visit
1.3 Schedule of Activities (SoA)	Pulmonary function test of FVC with spirometry Changed to Pulmonary function test with spirometry	For alignment with revised Exclusion Criterion 5.2
8 Study Assessments and Procedures, Screening Visit 1	Pulmonary function test (Spirometry to obtain FVC value) Changed to Pulmonary function test ( including Spirometry)	For alignment with revised Exclusion Criterion 5.2
1.3 Schedule of Activities (SoA), footnote e	Added text If the participant has not had the test performed within 3 years and is treated by and compliant with NIV, then this test is not required for eligibility.	For alignment with revised Exclusion Criterion 5.3
8 Study Assessments and Procedures, Screening Visit 1	Nocturnal Polysomnography (schedule a visit day for participants who have not taken the test within the last 3 years) Added text or who are not being treated by NIV	For alignment with revised Exclusion Criterion 5.3

Section # and Name	Description of Change	Brief Rationale
9.4 Statistical Analyses	The statistical analysis plan will be developed and finalized before database lock for the first cohort Deleted text for the first cohort	The database will not be locked for the first cohort, therefore the text was removed.
9.4 Statistical Analyses	Moved text from section 9.4.1 to 9.4.3: For the EEG, the analysis variables are the theta/alpha and theta/beta spectral ratios, along with the theta, alpha, and beta percentages. Additional exploratory parameters may be included in the analysis.	For alignment with the deletion of EEG from Secondary Endpoints
9.4.1 Efficacy Assessments	A mixed effect model will be used to compare efficacy effects (PVT, SSS, One-back, and EEG test) Deleted text and EEG test	For alignment with the deletion of EEG from Secondary Endpoints

**ABBREVIATIONS**

TERMS	DEFINITIONS
AE	Adverse event
ALT	Alanine aminotransferase
AST	Aspartate aminotransferase
BMI	Body mass index
BP	Blood pressure
CGI-I	Clinical Global Impression – Improvement scale
CFR	Code of federal regulations
CNS	Central nervous system
CONSORT	Consolidated Standards of Reporting Trials
CRF	Case report form
CSF	Cerebrospinal fluid
DNA	Deoxyribonucleic acid
DM1	Myotonic dystrophy type 1
ECG	Electrocardiogram
EEG	Electroencephalograph
EDS	Excessive daytime sleepiness
ESS	Epworth sleepiness scale
FDA	Food and Drug Administration
FSH	Follicle stimulating hormone
FVC	Force vital capacity
GABA A	Endogenous type A gamma-amino-butyric-acid
GCP	Good Clinical Practice
GGT	Gamma-glutamyl transferase
hCG	human chorionic gonadotropin
HIPAA	Health Insurance Portability and Accountability Act
HRT	Hormone replacement therapy
ICD	Implantable cardioverter defibrillator
ICF	Informed consent form
ICH	International Conference on Harmonisation
IEC	Independent Ethics Committee

---

TERMS	DEFINITIONS
IH	Idiopathic hypersomnia
IRB	Institutional Review Board
IUD	Intrauterine device
MCH	Mean corpuscular hemoglobin
MCV	Mean corpuscular volume
MDHI	Myotonic dystrophy health index
NIV	Non-invasive ventilation
PGI-I	Patient Global Impression – Improvement scale
PK	Pharmacokinetic
PR	PR interval
PVT	Psychomotor Vigilance Task
QRS	QRS interval
QT	QT interval
RBC	Red blood cell count
RT	Response time
SAE	Serious adverse event
SGOT	Serum Glutamic-Oxaloacetic Transaminase
SGPT	Serum Glutamic-Pyruvic Transaminase
SoA	Schedule of Assessments
SOC	System organ classification
SSS	Stanford Sleepiness Scale
TSH	Thyroid stimulating hormone
WBC	White blood cell count
WOBCP	Woman of child bearing potential

## 1. PROTOCOL SUMMARY

### 1.1. Synopsis

**Protocol Title:** Double-Blind, Placebo-Controlled, Dose-Range-Finding, Crossover Trial of Single Day Administration of ERX-963 in Adults with Myotonic Dystrophy Type 1

**Short Title:** Safety, Tolerability and Pharmacokinetics of ERX-963 in Adults with Myotonic Dystrophy Type 1

#### **Rationale:**

Myotonic dystrophy type 1 (DM1) is a multisystem disorder that includes central nervous system (CNS) involvement (Thornton-2014). The symptoms of CNS involvement include excessive daytime sleepiness (EDS) and cognitive dysfunction; these symptoms are recognized to have significant impact on quality of life (Heatwole-2012, Laberge-2013).

Dysregulation of the endogenous type A gamma-amino-butyric-acid (GABAA) neurotransmitter system is hypothesized to be a primary cause of EDS and cognitive dysfunction in patients with DM1. There are two potential factors that underlie GABAA dysregulation in DM1.

Firstly, patients with DM1 have an increased prevalence of the short form of the  $\gamma 2$  subunit of the GABAA receptor which may alter the sensitivity and activity of the receptor (Goodwin-2015). In the normal adult brain, the long isoform of the  $\gamma 2$  subunit predominates whereas in DM1, the fetal, or short, isoform predominates. The increase in the prevalence of the short isoform of the GABAA receptor  $\gamma 2$  subunit is a consequence of a broader mRNA splicing defect which is a well-characterized feature of DM1. The short isoform has been shown to have higher affinity to GABA compared to the long isoform ([name], Personal communication). Mice expressing only the short isoform exhibit increased sensitivity to benzodiazepines (Quinlan-2000). Secondly, DM1 may be associated with the presence of a somnogen (an endogenous substance with GABAergic like effects) in the cerebrospinal fluid (CSF) which has been observed in patients with idiopathic hypersomnia (IH) (Rye-2012). For an individual patient with DM1, either or both of these factors could contribute to the clinical presentation of EDS and cognitive dysfunction.

Because of the role of GABAA receptor dysfunction in DM1, it is hypothesized that [REDACTED] may reverse the sedative effect of the somnogen or normalize the activity of the GABAA  $\gamma 2$  short isoform. [REDACTED] is a selective benzodiazepine antagonist, administered intravenously, that is approved by the FDA and widely used to treat benzodiazepine overdose and reverse benzodiazepine effects in the context of conscious sedation or surgical anesthesia. Rye et al. (Rye-2012) and Trotti et al. (Trotti-2016) have reported that treatment with [REDACTED] can yield significant improvements in sleepiness and related symptoms in selected patients with IH. One of the IH patients who showed benefit with intravenous (IV) [REDACTED] (Rye-2012) was later diagnosed with DM1 ([name], Personal communication).

The safety and efficacy of ERX-963 (IV ██████████) to treat EDS/hypersomnia have not been formally evaluated in patients with DM1 in a placebo-controlled fashion. The purpose of this study therefore is primarily to investigate the safety and tolerability of ERX-963, and secondarily to evaluate its potential to reduce EDS/hypersomnia and improve cognitive function in patients diagnosed with DM1.

### Objectives and Endpoints:

Objectives	Endpoints
Primary	

 
To assess the safety and tolerability of a single dose of ERX-963 vs. placebo in patients with DM1
 
	
 
The proportion of participants with adverse events, serious adverse events (SAEs), and drug related adverse events
 

Secondary	

 
To assess the effect of intravenously-administered ERX-963 vs. placebo on sleepiness, vigilance, and working memory in patients with DM1
 
	Repeated measurements of the following: 
 
Stanford Sleepiness Scale (SSS) score
 
Psychomotor Vigilance Task (PVT) – No. of lapses and 1/Longest 10% Response time (1/RT) and median reaction time
 
One-back task – proportion of correct response
 
Clinical Global Impression – Improvement scale (CGI-I)
 
Patient Global Impression – Improvement scale (PGI-I)
 

Exploratory	

 
To correlate ERX-963 plasma concentrations to clinical efficacy endpoints in patients with DM1
 
To assess the effect of intravenously-administered ERX-963 vs. placebo on brain activity in patients with DM1
 
	Repeated measurements of the following: 
 
Plasma ERX-963 concentration
 
Stanford Sleepiness Scale (SSS) score
 
Psychomotor Vigilance Task (PVT) – No. of lapses and 1/Longest 10% Response time (1/RT) and median reaction time
 
One-back task – proportion of correct response
 
EEG – theta/alpha and theta/beta spectral ratios, and theta, alpha, and beta percentages
 

**Overall Design:**

This is a multi-center, randomized, double-blind, placebo-controlled, two-treatment period crossover study in two cohorts of participants with DM1.

Participants who have consented and meet eligibility criteria will receive two treatments, IV Placebo (Treatment A) and ERX-963 (Treatment B or C) in a randomized crossover fashion with approximately 4 to 18 days washout between the treatments (Note: washout days are counted from the day of dosing in Period 1). The study will be conducted in two cohorts.

In cohort 1, six (6) participants will be randomized to one of two sequences:

Sequence 1: Treatment A: IV Placebo in Period 1 →

4 to 18 days washout →

Treatment B: 1 mg ERX-963 in Period 2.

Sequence 2: Treatment B: 1 mg IV ERX-963 in Period 1 →

4 to 18 days washout →

Treatment A: IV Placebo in Period 2.

ERX-963 1 mg or placebo will be administered intravenously over 5 minutes.

In cohort 2, six (6) participants will be randomized to one of two sequences:

Sequence 1: Treatment A: IV Placebo in Period 1 →

4 to 18 days washout →

Treatment C: Selected ERX-963 dose in Period 2.

Sequence 2: Treatment C: Selected ERX-963 dose in Period 1 →

4 to 18 days washout →

Treatment A: IV Placebo in Period 2.

The selected ERX-963 dose (0.5 mg, 1 mg or 2 mg) or placebo will be administered intravenously over 5 minutes (0.5 mg or 1 mg) or 15 minutes (2 mg).

This study is evaluating single administration of two doses levels (1 mg and 0.5 or 2 mg) of ERX-963 to explore the relationship between dose, exposure and safety, tolerability and clinical benefit. Both dose levels to be evaluated in this study are within the FDA approved dose range of IV [REDACTED] and have been used with favorable safety and tolerability for over 25 years in clinical practice in the treatment of patients following benzodiazepine anesthesia and benzodiazepine overdose.

ERX-963 dose for cohort 2 will be selected based on a *blinded review* of safety data from cohort 1. A decision to proceed to cohort 2 with the planned 2 mg dose, to lower the dose to 1 mg or 0.5 mg, or cease dosing altogether, will be made jointly by the medical monitor and the principal investigators and will be based on the clinical nature of adverse events, safety laboratory and vital signs abnormalities observed during cohort 1 ([Section 6.6](#)).

**Disclosure Statement: This is a crossover treatment study with two cohorts that are blinded to the participant and investigator. Blinding of placebo and investigational drug is during randomization, drug administration, and assessment periods for each cohort.**

**Number of Participants:**

Approximately 20 potential participants will be screened to dose at least 6 participants in each cohort (for an estimated total of 14 participants completing the study). Participants who do not complete the crossover portion of the study will be discontinued and replaced with a new participant.

**Intervention Groups and Duration:**

[figure not shown]
The total duration of the study for an individual participant is approximately 57 days. The screening period is  $\leq 21$  days; the intervention and assessment in the two dosing periods will be conducted over 1 day with approximately 4 to 18 days washout period between the two periods. The follow up period is approximately 4 to 18 days.

The study will be conducted in two cohorts. Participants will receive two treatments in each cohort: IV Placebo (Treatment A) and ERX-963 (Treatment B or C) in a randomized crossover fashion.

**Data Monitoring Committee: No**

## 1.2. Schema

\* Outcome Measure Tests (OMT): Stanford Sleepiness Scale, Psychomotor Vigilance Task, One-back Test

**1.3. Schedule of Activities (SoA)**

Procedure	Screening Visit (up to 21 days before Period 1)	Intervention Period			End of Study (4-18 days after Period 2) or Early Discontinuation
		Period 1	Washout Period: 4-18 days	Period 2	
Informed consent	X				
Inclusion and exclusion criteria	X				
Medical history (including myotonic dystrophy diagnosis history)	X				
Medication history a	X				
Full physical examination and Demography including height and weight	X				
Brief physical exam		X b		X b	X
Vital signs (BP, Respiration Rate and Pulse Rate)	X	X c		X c	X
Laboratory assessments (hematology, clinical chemistries) 	X	X b		X b	X
Hepatitis C antibody test	X				
Plasma biomarker exploration (subjects who consented to provide the sample only)	X				
Serum pregnancy test (WOCBP only)	X				X
Urinalysis	X				X
12-lead ECG	X				
Pulmonary function test with spirometry	X				
MDHI, Epworth sleepiness scale (ESS)	X				
Actigraph d	X				
Polysomnograph e	X				
Outcome Measure Tests (Stanford sleepiness scale [SSS], Psychomotor vigilance task [PVT] and One-back test)	X f	X g		X g	
Randomization		X			
Video (subjects who consented only)		X h		X h	
EEG		X h		X h	
Study intervention (IV Infusion) k		X		X	
PK sampling		X i		X i	
CGI-I and PGI-I		X j		X j	

Procedure	Screening Visit (up to 21 days before Period 1)	Intervention Period			End of Study (4-18 days after Period 2) or Early Discontinuation
		Period 1	Washout Period: 4-18 days	Period 2	
AE review	X	X	←=====→		
Concomitant medication review		X	←=====→		

- a Prescription and non-prescription (over the counter, OTC) medications, herbal medications, vitamins, minerals and medications over the past 30 days. Lifetime history of medication taken for DM1 or sleep.
- b After completion of all assessments (after PGI-I is completed).
- c Pre-dose vital signs within 60 minutes prior to start of study intervention; post-dose vital signs after completion of all assessments (after PGI-I is completed).
- d To qualify participants per [inclusion criteria #3](#).
- e To be performed during screening period if participant has not had this test performed within 3 years. If the participant has not had the test performed within 3 years and is treated by and compliant with NIV, then this test is not required for eligibility.
- f Practice outcome measure tests and screening visit outcome measure tests with 20 minute rest in between.
- g Practice outcome measure tests and pre-dose baseline outcome measure tests with 20 minute rest in between prior to start of study intervention; Cohort 1 (1mg) and Cohort 2 (if selected dose is 0.5 or 1 mg): post-dose outcome measure tests at 15 minutes, 45 minutes, 1 hour 15 minutes and 1 hour 45 minutes after the start of study intervention. Cohort 2 (if selected dose is 2 mg): post-dose outcome measure tests at 25 minutes, 55 minutes, 1 hour 25 minutes and 1 hour 55 minutes after the start of study intervention.
- h Start video and EEG recording prior to practice outcome measures test until all the post-dose tests (last blood sample) has been completed.
- i Blood samples for Cohort 1 (1 mg) and Cohort 2 (if selected dose is 0.5 or 1 mg): at the end of 5 minute IV infusion and after conclusion of each set of outcome measure tests at approximately 30 minutes, 1 hour, 1 hour 30 minutes and at 2 hours after the start of IV infusion. Blood samples for Cohort 2 (if selected dose is 2 mg): at the end of 15 minute IV infusion and after conclusion of each set of outcome measure tests at approximately 40 minutes, 1 hour and 10 minutes, 1 hour 40 minutes and at 2 hours and 10 minutes after the start of IV infusion
- j After the video and EEG recordings are completed.
- k Cohort 1: ERX-963 1 mg or placebo will be administered intravenously over 5 minutes; Cohort 2: the selected ERX-963 dose (0.5 mg, 1 mg or 2 mg) or placebo will be administered intravenously over 5 minutes (0.5 mg or 1 mg) or 15 minutes (2 mg).
- l Fasting not required.

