## 4. STUDY DESIGN

### 4.1. Overall Design

This is a multi-center, randomized, double-blind, placebo-controlled, two-treatment crossover study in participants with DM1.

In this study participants who have consented and meet all-eligibility criteria will receive two treatments, IV Placebo (Treatment A) and ERX-963 (Treatment B or C) in a crossover fashion with approximately 4 to 18 days washout between the treatments (Note: washout days are counted from the day of dosing in Period 1). The study will be conducted in two cohorts.

In cohort 1, six (6) participants will be randomized to one of two sequences:

Sequence 1: Treatment A: IV Placebo in Period 1 →  
4 to 18 days washout →  
Treatment B: 1 mg ERX-963 in Period 2.

Sequence 2: Treatment B: 1 mg EX-963 in Period 1 →  
4 to 18 days washout →  
Treatment A: IV Placebo in Period 2.

ERX-963 1 mg or placebo will be administered intravenously over 5 minutes.

In cohort 2, six (6) participants will be randomized to one of two sequences:

Sequence 1: Treatment A: IV Placebo in Period 1 →  
4 to 18 days washout →  
Treatment C: Selected ERX-963 dose in Period 2.

Sequence 2: Treatment C: Selected ERX-963 dose in Period 1 →  
4 to 18 days washout →  
Treatment A: IV Placebo in Period 2.

The selected ERX-963 dose (0.5 mg, 1 mg or 2 mg) or placebo will be administered intravenously over 5 minutes (0.5 mg or 1 mg) or 15 minutes (2 mg).

ERX-963 dose for cohort 2 will be selected based on a *blinded review* of safety data from cohort 1. A decision to proceed to cohort 2 with the planned 2 mg dose, to lower the dose to 1 mg or 0.5 mg, or cease dosing altogether, will be made jointly by the medical monitor and the principal investigators and will be based on the clinical nature of adverse events, safety laboratory and vital signs abnormalities observed during cohort 1 (See [Section 6.6](#)).

Blinding of placebo and investigational drug will be maintained during randomization, drug administration, and complete assessment periods for each cohort.

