## 4.2. Scientific Rationale for Study Design

This Phase 1b study is designed to be a randomized, double-blind, placebo-controlled, two-treatment crossover trial comparing the safety, tolerability, and the exploratory endpoints evaluating the effectiveness of a single dose of ERX-963 (IV [REDACTED] versus IV placebo.

Since this is an exploratory study, it is designed as a two cohort study to allow for safety evaluation after completion of cohort 1 and prior to initiation of cohort 2.

This study is designed as a crossover trial in which participants will receive both ERX-963 and IV placebo with approximately 4 to 18 days washout in between the two treatments. A crossover design was chosen to allow participants to serve as their own controls, thus increasing the ability to detect clinical effects with a minimum number of participants. In each cohort, 6 participants will be randomized in a 1:1 ratio to receive two treatments in one of 2 treatment sequences (ERX-963 followed by placebo or placebo followed by ERX-963; 3 subjects/sequence) to balance for potential first-order carryover effects.

[REDACTED] half-life is reported to be 40-80 minutes ([REDACTED] [USPI-2018](#)). The exploratory end points and PK samples will be collected at half-hour intervals over a 2 hour period after dosing. The duration of assessment is based on prior experience suggesting that [REDACTED] effect lasts for about 2 hours ([Rye-2012](#)) which is consistent with its short half-life.

The PK sampling times have been selected to correlate serum [REDACTED] concentration to potential clinical improvement as measured by the efficacy endpoints.

Given the short half-life, the planned washout period of approximately 4 to 18 days would be more than sufficient to ensure both the drug and the drug's effects are completely cleared prior to dosing in the second period.

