## 6.6. Dose Modification

This is a single dose study and hence dose modification in cohort 1 is not applicable.

Intravenous [REDACTED] has been used for over two decades for reversal of benzodiazepine induced anesthetic sedation and management of benzodiazepine overdose with an acceptable safety profile. The 1 and 2 mg infusions of ERX-963 (IV [REDACTED] specified in this protocol are lower than the 5 mg maximal dose specified in the FDA approved [REDACTED] product label. Although it is anticipated that the safety profile of single doses of [REDACTED] in participants with DM1 will be similar to the established safety profile of [REDACTED] blinded review of safety (adverse events, safety laboratories and vital signs) will be performed following completion of cohort 1 and prior to initiation of cohort 2. A decision to proceed to cohort 2 with

the planned 2 mg dose, to lower the dose to 1 mg or 0.5 mg, or cease dosing altogether, will be made jointly by the medical monitor and the principal investigators and will be based on the clinical nature adverse events and/or safety laboratory abnormalities observed during cohort 1, their potential for relatedness to active study medication, and the degree of unexpectedness as compared to the existing known [REDACTED] safety profile.

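### The only scheduled post-dose vital signs on dosing days come nominally about 115 minutes after the infusion ends (about 1.4 to 2.9 stated half-lives), so the blinded Cohort 1 review and the SAP 12.3 table hold no scheduled reading near peak exposure

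*Protocol*

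**What the plan says.** Footnote c of the Schedule of Activities (Protocol 1.3) gives two vital-sign sets per dosing day. The first is described as "Pre-dose vital signs within 60 minutes prior to start of study intervention". The second is described as "post-dose vital signs after completion of all assessments (after PGI-I is completed". The evaluation-day list in Protocol section 8 and SAP 12.3 name the same two readings and no other.

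The second reading is late because of what comes before it. Footnote j places CGI-I and PGI-I as follows: "After the video and EEG recordings are completed". Footnote h keeps those recordings running "until all the post-dose tests (last blood sample) has been completed". Footnote i puts the last blood sample at about 2 hours after the start of a 5-minute infusion (0.5 or 1 mg), or 2 hours 10 minutes after the start of a 15-minute infusion (2 mg).

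Protocol 4.2 says of the drug that its "half-life is reported to be 40-80 minutes" and that its "effect lasts for about 2 hours". It uses this to justify half-hourly efficacy and PK measurements.

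Vital signs feed the choice of the Cohort 2 dose. Protocol 4.1 says the decision "will be based on the clinical nature of adverse events, safety laboratory and vital signs abnormalities observed during cohort 1". Protocol 6.6 says a "blinded review of safety (adverse events, safety laboratories and vital signs) will be performed following completion of cohort 1", although its own decision sentence then names only adverse events and laboratory findings. SAP 12.3 summarises vital signs and their change from pre-dose by treatment, with no test.

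**The concern.** Safety and tolerability are the primary objective, and Cohort 1 is reviewed before Cohort 2 may go to 2 mg. Efficacy and PK are followed through the period in which the protocol expects the drug to act. Pulse, blood pressure and respiration are read only as that period closes.

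A transient change without symptoms could come and go before the single post-dose reading. AE questioning cannot find a change the participant does not feel, and the only scheduled 12-lead ECG is at screening. If such a change occurred, neither the Cohort 1 review nor the SAP 12.3 table would be set up to show it. Protocol 2.2 notes that cardiac disease in myotonic dystrophy usually involves the conduction system, so pulse is a sensible thing to read near peak in this population.

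**Working it through.** **Check on the time scale.** SAP 14.1 states that the test batteries start 10, 40, 70 and 100 minutes after the end of administration in both schedules. This reproduces:
- 5-minute infusion: 15, 45, 75, 105 minus 5 = 10, 40, 70, 100.
- 15-minute infusion: 25, 55, 85, 115 minus 15 = 10, 40, 70, 100.

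**Time of the post-dose reading.** The last blood sample is at 120 − 5 = 115 minutes after infusion end (0.5 or 1 mg) and 130 − 15 = 115 minutes (2 mg). The figure is nominal, because sample times are approximate. Section 8 allows about 15 minutes per battery, but the components in 8.1.1 add to about 1 + 5 + 4 = 10 minutes, so the last sample could come at 100 + 10 = 110 minutes. Completing CGI-I and PGI-I pushes the reading the other way.

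**Exposure at that reading.** Half-lives elapsed = t / h. Fraction remaining = 2^(−t/h), assuming one-phase decay from the end of infusion.

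| Minutes after infusion end | Half-lives (h = 80 to 40 min) | Remaining (h = 80 to 40 min) |
|---|---|---|
| 5 | 0.06 to 0.13 | 96% to 92% |
| 10 | 0.13 to 0.25 | 92% to 84% |
| 25 | 0.31 to 0.63 | 81% to 65% |
| 110 | 1.38 to 2.75 | 39% to 15% |
| 115 (nominal) | 1.44 to 2.88 | 37% to 14% |
| 120 | 1.50 to 3.00 | 35% to 13% |

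Moving between 110 and 120 minutes does not change the picture. SAP 15.2 also allows a two-compartment profile. If 40 to 80 minutes is the terminal half-life, an added distribution phase would make every percentage in the table lower and the contrast between early and late readings at least as large.

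**Contrast with an earlier reading.**
- 5 to 10 minutes after infusion end: 2^(105/80) = 2.5 to 2^(110/40) = 6.7 times the concentration at the current reading.
- 25 minutes after: 2^(90/80) = 2.2 to 2^(90/40) = 4.8 times.

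**Length of the unread interval.** If section 8 is followed in its listed order, vital signs precede the practice battery, the rest and the baseline battery: 15 + 20 + 15 = 50 minutes before dosing. The two sets are then about 50 + 120 = 170 minutes apart (0.5 or 1 mg) or 50 + 130 = 180 minutes (2 mg), before time for CGI-I and PGI-I.

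**Does an early set fit?**
- Before the first battery there are 15 − 5 = 10 or 25 − 15 = 10 minutes. Protocol 8.2.2 requires 5 minutes of semi-supine rest, leaving 10 − 5 = 5 minutes for the blood draw and the reading together. With an assumed 2 minutes each, the total is 2 + 5 + 2 = 9 minutes. If draw and reading together exceed 5 minutes, the battery is late. If the rest is already met during the infusion, only 2 + 2 = 4 minutes are needed.
- After the 30-minute sample (0.5 or 1 mg) or 40-minute sample (2 mg) there are 45 − 30 = 15 or 55 − 40 = 15 minutes before the next battery. The same 9 minutes fit with room to spare.

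**Volume.** Two periods × 12 to 14 completers = 24 to 28 extra sets. Cohort 1 contributes 6 × 2 = 12.

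**The case against.** The strongest reply is that light monitoring is a reasonable choice for a known drug. Protocol 4.3 reports that the drug given alone was tolerated up to 100 mg over 5 minutes in healthy volunteers, which is 50 to 100 times the 2 mg and 1 mg doses. Protocol 2.2 places the rare rhythm disturbances in acutely ill overdose patients. Exclusion 2 removes low ejection fraction, heart rate below 60, an untreated pacemaker indication and implanted defibrillators. AEs are reviewed throughout the day, and nothing prevents an unscheduled reading. All of this stands, and it lowers the importance of the point. None of it supplies a systematic reading near peak in DM1 patients.

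The benefit to the dose decision is also limited. Reviewers are blinded, the protocol sets no vital-sign threshold, and with 6 exposed participants an effect present in 10% of patients would be absent from the sample with probability 0.9^6 = 53%. That is a fair limit on what the review can conclude. It does not argue for leaving the reading out.

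Finally, an added semi-supine rest just before the first Stanford Sleepiness Scale is not matched by one scheduled right before the baseline battery, and SAP 14 names that scale among the measures expected to be most sensitive. Handling could raise alertness; resting could lower it. A shift that is equal under both treatments cancels from the crossover contrast, but one that depends on treatment would not. This is why the early slot should be used only if it causes no delay, with a later slot as fallback.

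A reader might infer that participants are dosed without safety observation, or that the primary endpoint is compromised. The documents do not support either. Staff test participants repeatedly through the post-dose period, and the endpoint is the proportion with AEs, which does not depend on the vital-sign schedule unless a finding is judged clinically significant.

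**Conclusion.** The point holds as a gap in measurement timing. The single scheduled post-dose set falls nominally about 115 minutes after infusion end, roughly 110 at the earliest plausible nominal time. That is about 1.4 to 2.9 stated half-lives, with about 14% to 37% of the end-of-infusion concentration left at 115 minutes. The blinded Cohort 1 review and the SAP 12.3 table therefore rest on readings taken well after peak.

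The percentages assume one-phase decay and the half-life range in Protocol 4.2. The timing itself needs only the schedule.

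Two further inferences should be resisted. Nothing in the documents shows that pulse, blood pressure or respiration changes at 0.5 to 2 mg, so no specific hazard is established. Nor is there evidence that an early reading would have changed the Cohort 2 dose. The case for the change is that it costs little and serves the primary objective.

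**What to change.** In both periods, add one pulse, blood pressure and respiration set early after dosing, and keep the set after PGI-I unchanged.

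- **Preferred slot:** between the end-of-infusion blood sample and the first battery, only if the battery still starts on time. Keeping the participant semi-supine during the infusion would meet the 5-minute rest in advance.
- **Fallback slot:** just after the 30-minute (0.5 or 1 mg) or 40-minute (2 mg) blood sample, 25 minutes after infusion end, with about 65% to 81% of the end-of-infusion level remaining and about 15 minutes free.

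Use one slot throughout, so that the two periods are comparable, and place the cuff away from the sampling limb. No ECG is requested.

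Add the time point to footnote c, Protocol section 8, SAP 12.3 and the data for the blinded Cohort 1 review. Reviewers would see 12 unlabelled early sets; the ERX-963 versus placebo comparison would come only after unblinding.

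The cost is 24 to 28 routine sets and a small possible effect on alertness before one battery, expected to be the same under both treatments. Protocol 8.5 allows time points to be added with documented approval and no amendment, but that wording sits in the pharmacokinetics section. Since protocol text would be edited, allow for a minor amendment with ethics approval.
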